## 2 Rationale

### 2.1 Study rationale and purpose

The results from [CRAD001M2301] have shown that a significant proportion of patients with advanced TSC-associated SEGA benefited from continuous treatment with the mTOR inhibitor everolimus which led to volume reduction of the SEGA lesions. Patients with TSC-associated SEGA are typically young children at pre-pubertal age whose physical and sexual maturation is ongoing. mTOR has been shown to be an important regulator of cell growth and proliferation. Additionally, it is possible that mTOR is also a regulator of sexual development and maturation. As many patients treated in [CRAD001M2301] were young at the time of their exposure to everolimus (an mTOR inhibitor) and/or have experienced prolonged exposure to the drug from a young age, patients exposed to everolimus as part of CRAD001M2301 may present an appropriate study population in which to track the long term impact of everolimus exposure on growth and development.

Upon request by the EMA (during the procedure EMEA/H/C/002311/II/0004), this safety extension-study, classified as Post-Authorization Safety Study (PASS), is implemented to continue growth and development monitoring of pediatric patients enrolled in CRAD001M2301 who have been treated or are being treated with everolimus.

The study will monitor the growth and development of pediatric patients with TSC-associated SEGA, previously enrolled in CRAD001M2301 until they reach Tanner Stage V, or until age 16 for females or 17 for males whichever occurs first. After completion of [CRAD001M2301] continued treatment with everolimus is at investigator discretion and is not required for participation in CRAD001M2305. It is expected that some patients will cease treatment with everolimus upon completion of study CRAD001M2301, but most will opt for continued treatment with everolimus. Under either circumstance, the patients will be eligible for enrolment in study CRAD001M2305.

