The dates of all performed brain MRI scans that are done in the scope of the regular TSC SEGA follow-up will be collected at the annual visits. Brain MRI data will not be collected at this point but may be retrieved at a later date if technological advancements pertaining to predicting future cognitive abilities such as the development of the working memory arise.

Brain development will be assessed by determining the occurrence of TSC-Associated-Neuropsychiatric-Disorders (TAND) with an appropriate TAND Checklist at each annual visit.

The first study visit will occur 3 months after enrollment in CRAD001M2305 and the first annual visit one year ( $\pm 30$  days) after enrollment in CRAD001M2305. The 3-monthly visits can be performed per telephone unless a visit to the site is clinically indicated.

Patient participation in the study will be completed once the patient has achieved Tanner Stage V or age 16 for females, age 17 for males, whichever occurs first.

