### **7.1.3 Study completion**

Patients will meet the criteria for study completion upon demonstrating Tanner Stage V, or reaching age 16 (females) or age 17 (males), whichever comes first. Upon meeting the criteria for study completion, the patient should schedule an End of Study visit at the site. The End of Study visit cannot be completed via telephone contact.

Patients who discontinue commercial everolimus should continue study participation until meeting any of the aforementioned criteria for study completion. The discontinuation of everolimus will be recorded on the End of Treatment CRF page. Safety monitoring should be continued for at least 30 days following the last dose of everolimus.

Patients who complete the study, or discontinue the study early, should have the reason for exiting the study recorded on the Study Phase Completion Disposition CRF (SEC) page.

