#### **10.4.1.3 Tanner Stage**

Tanner Stage will include two components for boys, namely testis and pubic hair; and two components for girls: breast development and pubic hair.

Percentage of patients who will have reached Tanner Stage V by age 16 (for females) or age 17 (for males) will be provided, side by side, on the FAS Puberty of the studies CRADM2305 and TOSCA, along with 95% confidence intervals.

The relationship between the everolimus exposure and the Tanner Stage will be further explored in the CRAD001M2305 patients as detailed below:

- The percentage of patients who will have reached Tanner Stage V by age 16 (for females) or age 17 (for males) will be described in the different subgroups defined by duration of everolimus exposure. These subgroups will be defined in the Report and Analysis Plan.
- The duration of exposure and the age at start of everolimus will be summarized using descriptive statistics in the subgroups of patients who will reach and who will not reach Tanner Stage V by age 16 (for females) or age 17 (for males).
- A logistic regression including the duration of exposure and the age at the start of everolimus as continuous covariates may also be used to further explore if needed the relationship between the everolimus exposure and the achievement of Tanner Stage V by age 16 (for females) or age 17 (for males). Additional covariates (e.g. time normalized Cmin) might also be included in the model.

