2.1.2 Date of last administration of everolimus

For CRAD001M2305 patients, the date of last administration of everolimus is defined as the last date when a non-zero dose was administered and was recorded on the Everolimus prescription record CRF of the CRAD001M2305 study.

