3.6 Study treatment

For CRAD001M2305 patients, all data described below will be pooled with the corresponding data from Study CRAD001M2301 and will be summarized using the safety set.

The participation in this study does not require the administration of everolimus. In such cases in which the patient was taking everolimus, data collection (such as therapeutic drug trough level, duration of everolimus interruptions and everolimus prescribed dose) will only be recorded, when available.

For patients in Study CRAD001M2305, the duration of everolimus exposure and cumulative everolimus dose will be described using descriptive statistics on the Safety Set.

The total duration of everolimus exposure will be calculated as the total duration of everolimus exposure received while on Study CRAD001M2301 plus the total duration of (commercially supplied) everolimus exposure reported in Study CRAD001M2305.

Similarly, the cumulative dose of everolimus will be calculated as the cumulative everolimus dose received while on Study CRAD001M2301 plus the cumulative everolimus (commercially supplied) dose reported in Study CRAD001M2305.

All exposure data will be listed.

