3.8.2 Tanner Stage

For CRAD001M2305 patients, all data described below will be pooled with the corresponding data from Study CRAD001M2301.

Tanner Stage will include two components for boys (testis and pubic hair) and two components for girls (breast development and pubic hair).

Percentage of patients who will have reached Tanner Stage V by age 16 (for females) or age 17 (for males) will be provided, side by side, on the FAS Puberty of the studies CRAD001M2305 and TOSCA, along with 95% confidence intervals.

If the number of CRAD001M2305 patients is sufficient and notably high abnormality, the relationship between the everolimus exposure and the Tanner Stage will be further explored as detailed below:

- The percentage of patients who will have reached Tanner Stage V by age 16 (for females) or age 17 (for males) will be described in the different subgroups defined by duration of everolimus exposure. These subgroups are described in the Section 3.12.
- The duration of exposure and the age at start of everolimus will be summarized using descriptive statistics in the subgroups of patients who will reach and who will not reach Tanner Stage V by age 16 (for females) or age 17 (for males).
- A logistic regression including the duration of exposure and the age at the start of everolimus as continuous covariates may also be used to further explore if needed the relationship between the everolimus exposure and the achievement of Tanner Stage V by age 16 (for females) or age 17 (for males). Additional covariates (e.g. time normalized C_{min}) might also be included in the model.

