3.8.4 Handling of missing values/censoring/discontinuations

All missing data will simply be described as missing until not specified on appropriate tables/listings in particular for patients who will not have reached Tanner Stage V or the age of 16 years (for females) or the age of 17 years (for males) at the end of the CRAD001M2305 study or at the end of the TOSCA registry using the FAS Puberty or Height, BMI analysis using the FAS population.

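### The exploratory Stage V analyses use total everolimus duration although follow-up ends at Stage V, and the SAP leaves open which exposure end date applies to a child who exits on drug

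*SAP*

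**What the plan says.** Protocol 10.4.1.3 announces the analysis: "The relationship between the everolimus exposure and the Tanner Stage will be further explored in the CRAD001M2305 patients as detailed below". Three pieces follow: Stage V percentages by duration subgroup, duration and age at start in those who do and do not reach Stage V, and an optional model. The SAP 3.8.2 wording for the model is "A logistic regression including the duration of exposure and the age at the start of everolimus as continuous covariates may also be used". SAP 3.8.2 runs all three only if patient numbers are sufficient and abnormality is notably high, and defines neither condition. SAP 3.12 sets the bands at under 5, 5 to under 10, and 10 or more years.

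The exposure variable is cumulative. SAP 3.6: "The total duration of everolimus exposure will be calculated as the total duration of everolimus exposure received while on Study CRAD001M2301 plus" the commercial exposure reported in M2305. SAP 2.1.2: "the date of last administration of everolimus is defined as the last date when a non-zero dose was administered and was recorded on" the M2305 prescription form.

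Follow-up has an outcome-dependent end. Protocol 4.1: "Patient participation in the study will be completed once the patient has achieved Tanner Stage V or age 16 for females", with 17 for males, whichever is first; protocol 7.1.3 agrees. On treatment, protocol 2.1 expects that "some patients will cease treatment with everolimus upon completion of study CRAD001M2301, but most will opt for continued treatment with everolimus".

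A second end-date rule sits in SAP 2.2 and 5.1.1 (Scenario 1). A dose record with no end date, no End of Treatment page and no death date is run to the cut-off, which is last patient last visit. SAP section 4 changes the pharmacokinetic and indirect comparison analyses but leaves these in place.

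**The concern.** A covariate meant to explain Stage V should be fixed before Stage V can act on it. Here, reaching Stage V ends participation and therefore ends the counting of exposure. Children who do not reach it keep accruing exposure to 16 or 17. Total duration can then be longer in non-reachers simply because they were observed for longer. Adjusting for age at start does not help, because start age and duration together reconstruct exit age.

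At stake is the interpretation of a secondary look at the study's own safety question. If the condition in SAP 3.8.2 is met, that is when the data already look abnormal, and an apparent duration relation would then be most persuasive.

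**Working it through.** The documents give no figure for these analyses (the SAP 3.13 tables concern low height), so there is none to reproduce.

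**1. The dependence.** SAP 5.1.2 defines duration as last date minus first date plus 1. For a child on drug to exit, age at start + duration ≈ exit age. As an illustration, take two girls who start at age 6. One has not reached Stage V and leaves at 16: duration 16 − 6 = 10 years. The other is found at Stage V at a visit at age 15: duration 15 − 6 = 9 years. Within sex, an exit age below the limit at study completion means that Stage V was reached. Annual detection softens this, because some reachers also exit at the limit. Protocol 10.3 takes interruptions into account and the SAP 5.1.2 formula does not; deducting them makes the identity approximate.

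**2. Size if exposure ends at the last recorded dose.** This was simulated with no drug effect and very large samples, fitting Stage V by 16/17 on duration and age at start. Assumptions not in the documents: start age 1–11; 3.3–5.3 years on drug at M2305 enrolment; Stage V age SD 1.2 with the means shown (girls/boys); annual detection; stop times independent of Stage V age.

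| Treatment pattern | Null OR per year, means 15/16 | Means 14.2/15.2 |
|---|---|---|
| All continue, no interruption | 0.22 | 0.16 |
| 80% continue, stops at M2305 entry | 0.88–0.89 | about 0.76 |
| 80% continue, stops spread over follow-up | about 0.67 | about 0.48 |
| 60% continue, stops at entry | 0.94–0.95 | 0.90 |
| 60% continue, stops spread | about 0.84 | about 0.70 |

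Variations, with means 15/16:
- Interruptions averaging 10% of time, if deducted, move 0.22 to about 0.41; the 80% at-entry figure hardly changes.
- SAP 3.8.4 says "All missing data will simply be described as missing until not specified on appropriate tables/listings in particular for patients who will not have reached" Stage V or the age limit. With 20% assigned an early leaving time and set to missing, the ORs are 0.21 (all continue), 0.88 and 0.66 (80%, stops at entry and spread), and 0.94 and 0.83 (60%).
- Adding sex (80% continuing) gives 0.88 (stops at entry) and 0.60 (spread).
- Other assumptions (overall Stage V mean 14.5–16, SD 1.0–1.3, enrolment age 5–15.5, 3–6 years of prior exposure) give 0.13–0.29, 0.37–0.80 and 0.70–0.94 when 0%, 20% and 50% stop early.

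Descriptive tables, 80% continuing with stops at entry: mean duration is 8.7 years in reachers and 9.3 in non-reachers. Stage V rates across the three bands are about 81, 81 and 77%, so the bands barely move.

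**3. Size if open records run to cut-off.** Assumed cut-off: 12.5 years after first enrolment. If 10–25% of children who exit on drug have open records, the OR is about 0.86–0.98; if 25–100%, it is 0.91–1.04. Those children are credited on average with 6–7 years after exit. Under the other assumptions in step 2, with every such record run to cut-off, the OR is 0.99–1.08 when 20–80% stop early but 0.66–0.84 when none do. The artefact therefore mostly goes, though not in every setting.

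**4. Check of the fix.** Count exposure only to age 12 (illustrative), in children enrolled and not yet Stage V at 12. The null OR becomes 0.996–1.011 (ages 11–13: 0.995–1.014; start ages 4–12: 0.979–1.017). The bands read 80/80/80% and the means 6.9 and 6.9 years. If all continue, exposure to 12 equals 12 minus age at start, so the two covariates are collinear; exposure alone then gives 0.992–1.001. The share of patients contributing is 54% (start ages 4–12), 70% (1–11) or 99% (1–7): 15 × 0.54 = 8.1, 15 × 0.70 = 10.5, 15 × 0.99 = 14.9.

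**The case against.** The best defence is that little rides on this. The analyses are conditional, the model is optional, and SAP 2.4.2.1 plans no test for the percentage rates. SAP 4.2 regards 15 patients as too few for the TOSCA comparison. In the pattern that protocol 2.1 describes, with stops on leaving the parent study, the bias is small against noise. Taking 3 non-reachers, 12 reachers and an SD of about 3.6 years, the SE of the difference in mean duration is 3.6 × √(1/3 + 1/12) = 2.3 years, about four times the 0.6-year artefact. All of this stands, and it limits the importance of the point.

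It is also fair that the artefact depends on the end-date rule. Protocol 7.1.3 ties the End of Treatment page to stopping everolimus, so a child who exits on drug may have none, and Scenario 1 could then apply. The share is unknown because the form is not in the documents. This does not rescue the plan: one rule lets the outcome shorten the exposure, and the other counts exposure nobody observed, after the outcome.

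A fixed age does discard exposure during puberty, which is a real loss. An age-scale model with time-varying exposure would keep it, but is out of proportion with 15 patients.

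**Conclusion.** The point holds in a limited form. With exposure ended at the last recorded dose, the optional logistic model and the mean-duration contrast lean towards longer exposure with less maturation when there is no drug effect. The direction was the same in every such scenario tried. The size rests on ages and stopping patterns that the documents do not give: about 0.88–0.95 per year with stops at entry and 0.67–0.84 with stops spread (60–80% continuing, Stage V means 15/16), and further from 1 if Stage V comes earlier. With open records run to cut-off, the lean mostly goes and post-outcome exposure replaces it. The SAP does not choose between the two rules.

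A reader might infer three stronger things that the documents do not support:
- That an OR near 0.22 is to be expected. It needs every child to continue without interruption, whereas protocol 2.1 expects some to stop.
- That the study will report a false harm signal. The analyses may never be run.
- That the primary Stage V percentage is biased. It does not use duration at all.

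The height, BMI, delayed-puberty and Cmin analyses were not examined here.

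**What to change.** 1. Reconcile SAP 2.1.2 and 3.6 with SAP 2.2 and 5.1.1 for children who exit on drug. State that exposure after Stage V or study exit is not counted in the 3.8.2 analyses.
2. If the condition in 3.8.2 is met, count exposure only up to one pre-stated age, in children enrolled and not yet Stage V at that age, for the duration tables and any model. Enter exposure and age at start together only if enough children stopped before that age; otherwise enter one. Redefine the duration bands, as SAP 3.12 allows. Say whether early leavers are left out of the model as missing. List the departure from protocol 10.4.1.3 in SAP section 4.
3. With 15 patients, report these results descriptively, and note that total duration by Stage V status is affected by the exit rule. Total duration can stay as the exposure description in SAP 3.6.

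The cost is SAP wording and programming, with no new data. The downside is that later exposure goes unused, its range narrows, and roughly 8 to 15 of the 15 patients contribute under the assumed start ages. A time-varying age-scale model is not needed at this sample size.

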3.8.3 Endocrine parameters

For CRAD001M2305 patients, all data described below will be pooled with the corresponding data from Study CRAD001M2301. Endocrine parameters such as LH, FSH, testosterone levels (in males) and LH, FSH, estrogen levels (in females) will be summarized descriptively, by study, by gender and by age over time on the FAS of the studies CRAD001M2305 and TOSCA.

Individual patient graphs over time will be provided for the CRAD001M2305 patients.

All data will be listed.

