#### **Primary endpoints:**

Growth and development of pediatric patients with TSC-associated SEGA who are taking everolimus or have previously taken everolimus will be monitored via:

- Percentage of patients who achieved Tanner Stage V by age 16 (for females) or age 17 (for males)
- Height, standard deviation score by year since baseline

- BMI, standard deviation score by year since baseline
- Mean endocrine laboratory values (FSH, LH, and estrogen or testosterone) by age

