### **7.2.2.3 Endocrine testing**

A blood sample for analysis of luteinizing hormone (LH), follicular stimulating hormone (FSH), and estrogen (females) or total testosterone (males) will be collected on day 1, annually, and at end of study for endocrine assessment at a local laboratory for all patients, starting at age 10 until study participation is ended. In the event that amenorrhea is reported in between scheduled assessments, hormone evaluations should be completed at that time.

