2.1.6.1 Growth data/ Endocrine data

Height and weight were collected at screening/baseline, every 4 weeks until Week 12, every 6 weeks until Week 24, every 12 weeks until EOT in the CRAD001M2301 study. The growth data (height and BMI) will be collected at the enrollment and every year until EOT in the CRAD001M2305 study. The growth data will be collected at the baseline and annually if available in the TOSCA study.

The endocrine data (LH, FSH, testosterone (in males) and LH, FSH, estrogen (in females)) will be collected in the CRAD001M2305 study at the baseline and then yearly, hence corresponding data will be pooled from CRAD001M2301 Study. The endocrine data will be collected in the TOSCA study at enrollment and annually if available.

Table 2-1 summarizes the time windows for Growth data/Endocrine data analyses, where windows are centered at every year after start of everolimus for CRAD001M2305 patients and every year after the enrollment date for TOSCA patients.

Table 2-1 Time windows for Growth data/ Endocrine data

Time Window	Planned Assessment Day		Time Window Definition	
	CRAD001M2305	TOSCA	CRAD001M2305	TOSCA
Baseline	Last available assessment on or before the start of everolimus in the parent study CRAD001M2301	First available assessment after the enrollment date	Before or on Treatment Day 1	Between Study Day 1 and Study Day 182
Year 1	Treatment Day 365	Study Day 365	Treatment Days 183 to 547	Study Days 183 to 547
Year 2	Treatment Day 730	Study Day 730	Treatment Days 548 to 913	Study Days 548 to 913
Year 3	Treatment Day 1096	Study Day 1096	Treatment Days 914 to 1279	Study Days 914 to 1279
Year 4	Treatment Day 1461	Study Day 1461	Treatment Days 1279 to 1644	Study Days 1279 to 1644
Every year thereafter until the end of each study				

Growth data, if more than one assessment is done within the Baseline time window, the assessment closest to study day 1 (for TOSCA) or treatment day 1 (for CRAD001M2301) will be used; if two or more assessments are equidistant from day 1, then the mean value will be used. For all other time windows, the assessment closest to the planned assessment date will be used; if two or more assessments are equidistant from the planned date, then the mean value will be used.

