3.8 Primary objective

The primary objective of this study is to report the effect of everolimus on height, BMI and sexual development (using Tanner Stages) in children and adolescents with TSC-associated SEGA who are taking everolimus or have taken everolimus.

To monitor the growth and the development of pediatric patients the following measurements will be performed annually:

- Height
- Weight
- Tanner Stage
- LH, FSH, and estrogen levels for female patients (for the CRAD001M2305 study, collected only for patients of 10 years old or older during the study)
- LH, FSH, and testosterone levels for male patients (for the CRAD001M2305 study, collected only for patients of 10 years old or older during the study)

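### The side-by-side hormone means by age can read slightly low for M2305 at about ages 14 to 16 with no drug effect, because M2305 sampling ends at Tanner V and no such rule is stated for TOSCA

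*SAP*

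**What the plan says.** - **Endpoint.** Protocol section 3 lists among the primary endpoints "Mean endocrine laboratory values (FSH, LH, and estrogen or testosterone) by age".
- **Display.** SAP 3.8.3 has the hormones "will be summarized descriptively, by study, by gender and by age over time on the FAS of the studies CRAD001M2305 and TOSCA". Protocol 10.4.1.4 plans the same summary with the two studies side by side. Neither conditions it on Tanner stage, and the SAP does not define the age bands.
- **M2305 entry.** Protocol 5.1 and 5.2 admit only children who have not reached Tanner V.
- **M2305 exit.** Protocol 4.1: "Patient participation in the study will be completed once the patient has achieved Tanner Stage V or age 16 for females" (17 for males), whichever comes first. Under Protocol 7.2.2.2, stage 5 on either component is enough.
- **M2305 sampling.** Protocol 7.2.2.3: samples "will be collected on day 1, annually, and at end of study for endocrine assessment at a local laboratory". The same section begins this at the tenth birthday and stops it when the child leaves the study.
- **Parent-study samples.** SAP 3.8.3 pools the M2301 hormone data of the same patients. SAP 2.1.5 explains that M2301 collected them from its amendment 2 onward.
- **TOSCA.** SAP 2.1.6.1: "The endocrine data will be collected in the TOSCA study at enrollment and annually if available". SAP 2.3.1 limits the TOSCA FAS by age at entry (below 16 for girls, below 17 for boys) and by absence of mTOR inhibitor use. It states no restriction on Tanner stage at entry or during follow-up.

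**The concern.** Whether a child can still give a sample at a given age depends, in M2305, on how mature the child already is. A child who reaches Tanner V at 14 gives one exit sample and then nothing at 15 or 16, so the older M2305 cells hold later maturers plus children sampled once on their way out. On the rules stated, a TOSCA child who is mature at 14 can stay in the 15- and 16-year cells. If sex-hormone levels are higher at Tanner V than before it, the M2305 column reads low at those ages even if everolimus does nothing.

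That pattern resembles delayed maturation, which the study was set up to look for. The display also carries more weight than it once did. SAP 4.2 judges the indirect comparison not meaningful with 15 patients, and that comparison was the one place where baseline Tanner stage was listed as a balancing covariate (SAP 3.9.3). The side-by-side tables are the main remaining contrast with untreated patients, and SAP section 1 says they should help separate the effect of TSC from that of everolimus.

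**Working it through.** The documents give no expected value, SD or sample size for the hormone endpoint, so there is no figure of the plan's own to reproduce. The size has to be modelled.

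**Inputs from the documents:** entry below Tanner V; exit at Tanner V or age 16/17; annual samples plus an end-of-study sample; no Tanner V rule stated for TOSCA.

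**Assumptions, not in the documents:** age at Tanner V is normal with mean mu = 14 to 16 years and SD 1.0 to 1.3 years (distribution function F). The mean hormone level at Tanner V is r = 1.5 to 2 times the level before it. There is no drug effect, and TOSCA samples are available regardless of stage.

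**Formulas at age a**
- Share of TOSCA samples at Tanner V: T = F(a).
- Share of M2305 samples at Tanner V, with annual visits and the exit sample kept: S = [F(a) - F(a-1)] / [1 - F(a-1)].
- Ratio of means, M2305/TOSCA: [1 + (r-1)S] / [1 + (r-1)T].

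**Age 16**

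| mu, SD | T = F(16) | F(15) | S | ratio, r = 1.5 | ratio, r = 2 |
|---|---|---|---|---|---|
| 14, 1.0 | 0.977 | 0.841 | 0.857 | 0.96 | 0.94 |
| 15, 1.3 | 0.779 | 0.500 | 0.558 | 0.92 | 0.88 |
| 16, 1.0 | 0.500 | 0.159 | 0.406 | 0.96 | 0.94 |
| 16, 1.3 | 0.500 | 0.221 | 0.358 | 0.94 | 0.91 |

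Example, second row with r = 2: (1 + 0.558)/(1 + 0.779) = 0.88.

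**Over the whole assumed range:** 1.00 at ages 10-11, 0.96-1.00 at 13, 0.91-1.00 at 14, 0.88-0.99 at 15 and 0.88-0.96 at 16. At age 16 the M2305 mean is therefore about 4-12% low.

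**Smooth-rise check.** A simulation in which the level climbs gradually towards Tanner V, instead of stepping up, gives 0.96 at age 16. That is the mild end of the range.

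**Role of the exit sample.** With no sample at Tanner V, S = 0 and the age-16 ratio would be 1/[1 + (r-1)T] = 0.51-0.80. Protocol 7.2.2.3 does require an end-of-study sample, so this larger shortfall is not what the plan produces.

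**Pooled M2301 samples.** These come from children still below Tanner V when M2301 ended, so they do not bring mature children back. Where they fall in the older cells they push the M2305 mean the same way. The documents do not give the mix, so I have not sized this.

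**Random error.** SAP 4.2 gives 15 patients. Assuming a between-child coefficient of variation of 40-80% and 3-7 children per sex-by-age cell, the standard error of a cell mean runs from 40%/√7 = 15% to 80%/√3 = 46%.

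**The case against.** The strongest reply is that the effect is small and nobody will rely on these means alone. The exit sample is kept. The display is descriptive, and SAP 4.2 already calls 15 patients too few for any comparison. Individual graphs and listings are planned (SAP 3.8.3), Tanner stage is reported separately (SAP 3.8.2), and potential delayed-puberty cases are clinically reviewed (SAP 3.9.2). This stands as far as severity goes: chance will probably swamp a 4-12% shift in any one cell. It does not remove the point, because the shift has a predictable direction, it resembles the safety signal of interest, and the SAP does not warn of it.

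A second reply is that the absence of a TOSCA limit is read from silence. That also stands. The TOSCA protocol is not among the documents, and samples taken only when available may be selective in either direction.

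Two stronger readings are tempting but not supported:

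- **The age-10 start adds to the low reading.** SAP 3.8 says hormones are "collected only for patients of 10 years old or older during the study". A by-age table compares children of the same age, so a start at 10 cannot change the means at 14-16; starting at age 0 in the simulation left every ratio from 10 to 16 unchanged. Nor is the analysed data set limited to age 10 and over, since no such limit is stated for the pooled M2301 samples.
- **A single cell for ages up to 12 would set M2305 children against TOSCA infants.** The split at 12 in SAP 3.2 is for demographics, and neither document applies it to hormones.

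**Conclusion.** The point holds in a limited form. M2305 entry and exit depend on Tanner V, no matching rule is stated for TOSCA, and the by-age hormone means are set beside each other without regard to stage. With no drug effect, the M2305 means can read low at about ages 14 to 16, by roughly 4-12% at age 16 with the exit sample kept.

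The direction requires hormone levels to be higher at Tanner V than before it, and TOSCA samples not to be selected by maturity. The size rests on the assumed timing of Tanner V (mean 14-16 years, SD 1.0-1.3) and the assumed level ratio (1.5-2). One range was used for both sexes. For girls, M2305 ends at 16, so age 16 means the exit visit. TOSCA samples beyond the 16/17 cap have no M2305 counterpart, which is lack of overlap and not a low reading.

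A reader might infer that all mature children are missing from M2305 and that the shortfall is 20-49%. The end-of-study sample rules that out. With 15 patients the bias is probably smaller than the random error per cell. This is a minor point and a cheap improvement.

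**What to change.** In SAP 3.8.3, for the side-by-side display:

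1. Exclude TOSCA patients already at Tanner V at entry. Include TOSCA samples only up to and including the first Tanner V visit or age 16 (girls) / 17 (boys), using the either-component rule of Protocol 7.2.2.2.
2. Tabulate by sex and one-year age band, so that by age is defined.
3. Add a table of hormone values by sex and concurrent Tanner stage. SAP Table 2-2 shows that both studies contribute hormones and Tanner stage. Give samples with no stage on record their own row.
4. Note the different entry and follow-up rules of the two studies as a limitation, including that M2301 samples come from children still below Tanner V when that study ended.

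No restriction to age 10 and over is needed; it would discard pooled M2301 samples without affecting the bias at 14-16.

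The cost is SAP wording and one extra table, with no new data collection. Some TOSCA samples leave the display, but they can still be listed. If the sponsor wants less, the Tanner-stage table with the limitation sentence would cover most of the problem.
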